Adverse Events Assessment	X	X	All SAEs must be collected that occur within 100 days of the last dose of study drug(s). All nonserious adverse events (not only those deemed to be treatment-related) should be collected for a minimum of 100 days following discontinuation of study treatment. Every adverse event must be assessed by the investigator with regard to whether it is considered immune-mediated. For events which are potentially immune-mediated, additional information will be collected on the subject's case report form.
Laboratory Tests	X		Perform Lab tests for Follow-up Visit 1 and repeat at Follow-up Visit 2, if any study drug toxicity persists. CBC w/differential, LFTs, BUN or serum urea level, creatinine, glucose, amylase, lipase, TSH (with reflexive Free T4 and Free T3).
Pregnancy Test (WOCBP Only)	X		Serum or urine
████████████████████	█		████████████████████
Document any current treatment regimen	X	X	To include immuno-therapy, chemotherapy, targeted therapy, radiotherapy, surgery, and all interventions to treat metastatic melanoma.
Survival Status		X	
Subject Status	X	X	Every 3 months, may be accomplished by visit or phone contact, to include subsequent anti-cancer therapy
████████████████████	█		████████████████████

Table 5.1-4: Follow-up Assessments (CA209204)			
Procedure	Follow-Up^a Visits 1 and 2	Survival^b Follow-up Visits	Notes Follow up is 3 years from start of treatment.
Efficacy Assessments			
Tumor Assessments	X		
Only for subjects who have not progressed on study therapy or who have discontinued study treatment for reasons other than documented disease progression.
 
Section 5.4
 
CT/MRI of chest, abdomen, pelvis and brain (MRI)
 
FIRST tumor assessment should first be performed at 6 weeks (± 7 days) from first dose date.
 
SUBSEQUENT tumor assessments should occur every 6 weeks (± 7 days) up to first 12 months (week 48), then every 12 weeks (± 7 days) until documented disease progression.

██████████	█		
████████████████████	█	█	████████████████████

^a Follow-up Visit 1 = 30 days from the last dose +/- 7 days or coincide with the date of discontinuation (+/- 7 days) if date of discontinuation is greater than 37 days after last dose, Follow-up visit 2 = 84 days (+/- 7 days) from follow-up visit 1

^b Survival visits = every 3 months from Follow-up Visit 2 +/- 7 days

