4 ENDPOINTS

4.1 Primary Endpoints

The primary endpoint is intracranial CBR. It is defined as the proportion of all treated subjects whose best overall response (BOR) is either a CR or PR or whose BOR was SD with duration of ≥ 6 months, as determined by modified RECIST 1.1 criteria for index intracranial lesions based on investigator review.

The BOR is defined as the best response designation recorded between the date of first study dosing date and the date of progression, or the date of subsequent anticancer therapy (including tumor-directed radiotherapy and tumor-directed surgery), whichever occurs first. In this study, BOR is specified for the intracranial, extracranial, and global compartments based on the (1) modified RECIST 1.1 criteria (intracranial), (2) RECIST 1.1 criteria (extracranial), (3) combination of modified RECIST 1.1 criteria and RECIST 1.1 criteria (global). Best response determination in trials where confirmation of complete or partial response is required: Complete or partial responses may be claimed only if the criteria for each are met at a subsequent time point as specified in protocol Appendix 3. There is no confirmation requirement for progressive disease (PD). The BOR for each patient as determined by the BICR is determined from a predefined set of rules specified within the Image Review Charter.

To ensure the accuracy of primary endpoints, analyses will be based on two sets of BOR: BOR as reported in the CRF and BOR with adjustment. BOR as reported in the CRF uses information entered in the CRF directly by investigators without adjustment. Results based on BOR with adjustments will serve as primary analysis. This decision was made after the interim database lock on 09 August 2020.

BOR with adjustment uses information entered in the CRF with the following adjustments:

- If BOR is NE, and the radiographic progression date is non-missing and prior to subsequent anti-cancer therapy start date, or subsequent anti-cancer therapy start date is missing, change BOR to PD.
- If BOR is SD, and the radiographic progression date is non-missing and duration of SD is less than 6 months and radiographic progression date is prior to subsequent anti-cancer therapy start date, or subsequent anti-cancer therapy start date is missing, change BOR to PD.
- If BOR is PR or CR, and there is preceding (confirmed or unconfirmed) PD and

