7.5.2.8 Progression Free Survival

The intracranial, extracranial and global PFS will be estimated using the Kaplan-Meier product-limit method, together with a two-sided 95% confidence interval for the median, calculated using the method of Brookmeyer and Crowley method.

PFS rates at 6, 12, 18, 24, 36, 48 months, and then every year will be estimated using KM estimates on the PFS curve. Minimum follow-up must be longer than the timepoint to generate the rate. Associated two-sided 95% CIs will be calculated. Results will be tabulated and plotted.

The source of progression event (death versus progression) will be summarized.

The status of subjects who are censored in the PFS KM analysis will be tabulated using the following categories:

- On-study (on-treatment, in follow-up)
- Off-study (lost to follow-up, withdrawn consent, never treated)
- Received subsequent anticancer therapy

All PFS data will be listed. In addition, a listing of subjects who were treated beyond progression will also be presented.

Sensitivity analyses using BICR-assessed PFS (intracranial, extracranial, and global) will also be performed for the above analyses and BICR PFS data will be listed.

In addition, to assess consistency of treatment effect in PFS in different subgroups, a ‘forest’ plot of the PFS rate at 6 month and two-sided 95% CIs based on Kaplan-Meier estimates will be produced on intracranial, extracranial and global PFS for the same variables as in section 7.5.2.2.

Primary censoring rules for the analysis of PFS are presented in Table 7.5.2.8-1.

Table 7.5.2.8-1: Censoring Scheme for Primary Definition of PFS

Situation	Date of Progression or Censoring	Outcome
No baseline tumor assessment	Date of first study treatment	Censored
No on-study tumor assessments and no death	Date of first study treatment	Censored
Documented progression	Date of first documented progression per RECIST 1.1 (excludes clinical progression)	Progressed
No progression and no death	Date of last evaluable tumor assessment	Censored
New anticancer therapy, tumor-directed radiotherapy, or tumor-directed surgery received without progression reported prior or on the same day	Date of last evaluable tumor assessment prior to initiation of subsequent therapy	Censored
Death without progression	Date of death	Progressed

[REDACTED]

In addition, a categorical summary of DOR will be presented for intracranial, extracranial and

[REDACTED]

[REDACTED]

[REDACTED]

[REDACTED]

[REDACTED]

[REDACTED]

[REDACTED]

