8.1.2 Partial Date Imputation

The following conventions may be used for imputing partial dates for analyses requiring dates:

For missing and partial AE onset dates, imputation will be performed using the Adverse Event Domain Requirements Specification. Missing and partial Non-Study Medication Domain dates will be imputed using the derivation algorithm described in BMS Non-Study Medication Domain Requirements Specification.

For death dates, the following conventions will be used for imputing partial dates:

- If only the day of the month is missing, the 1st of the month will be used to replace the missing day. The imputed date will be compared to the last known date alive + 1 day and the maximum will be considered as the death date.
- If the month or the year is missing, the death date will be imputed as the last known date alive + 1 day
- If the date is completely missing but the reason for death is present the death date will be imputed as the last known date alive + 1 day
- For date of progression, the following conventions will be used for imputing partial dates:
- If only the day of the month is missing, the 1st of the month will be used to replace the missing day*.
- If the day and month are missing or a date is completely missing, it will be considered as missing.
- * In case, the date of death is present and complete, the imputed progression date will be compared to the date of death. The minimum of the imputed progression date and date of death will be considered as the date of progression.
- For other partial/missing dates, the following conventions will be used:
- If only the day of the month is missing, the 15th of the month will be used to replace the missing day.
- If both the day and the month are missing, “July 1” will be used to replace the missing information.
- If a date is completely missing, it will be considered as missing.

The following conversion factors will be used to convert days to months or years: 1 month = 30.4375 days and 1 year = 365.25 days.

Duration (e.g. time from first diagnosis of Non-small Cell Lung Cancer (NSCLC) to first dosing date, duration response, and time to response) will be calculated as follows:

$$\text{Duration} = (\text{Last date} - \text{first date} + 1)$$

Last known date alive will be defined based on all appropriate dates collected on the CRF.

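### SAP 8.1.2 has no rule for incomplete radiotherapy and surgery dates; the default (15th or 1 July) can place therapy before the progression it followed, turning a PFS event into a censoring

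*SAP*

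**What the plan says.** SAP 8.1.2 sorts incomplete dates by type.

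- Adverse event onset dates go to an external specification. So do medication dates: "Missing and partial Non-Study Medication Domain dates will be imputed using the derivation algorithm described in BMS Non-Study Medication Domain Requirements Specification".
- Death dates have their own rule with a cross-check: "The imputed date will be compared to the last known date alive + 1 day and the maximum will be considered as the death date".
- Progression dates have their own rule and are capped at a complete death date.
- Everything else falls to a default, introduced by "For other partial/missing dates, the following conventions will be used". Where the day alone is absent, the SAP rule reads "If only the day of the month is missing, the 15th of the month will be used to replace the missing day". Where the month is absent too, it reads "If both the day and the month are missing, “July 1” will be used to replace the missing information". The default is compared with no other date.

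Radiotherapy and surgery dates are not named in 8.1.2. SAP 7.5.2.7 lists both apart from the items reported by drug name.

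Two places use these dates to decide which event came first. In SAP Table 7.5.2.8-1 the row "New anticancer therapy, tumor-directed radiotherapy, or tumor-directed surgery received without progression reported prior or on the same day" is censored at the last evaluable scan before the therapy. SAP 4.1 ends the best overall response (BOR) window at progression "or the date of subsequent anticancer therapy (including tumor-directed radiotherapy and tumor-directed surgery), whichever occurs first".

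The protocol (Section 3.1) allows a single episode of stereotactic radiotherapy (SRT) for progression in up to 3 intracranial lesions. In Protocol Table 5.1-4, subject status in follow-up is collected as follows: "Every 3 months, may be accomplished by visit or phone contact, to include subsequent anti-cancer therapy".

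**The concern.** Radiotherapy in this trial is often given because of a progression, so the two dates can lie close together. An imputation that ignores the progression date can reverse them. When therapy truly came second, the error runs one way only: a documented PFS event becomes a censoring at an earlier scan, and the censoring is caused by the progression itself. That is informative and raises the Kaplan-Meier estimate. Intracranial PFS (radiotherapy for brain progression) and global PFS are the most exposed. With the month missing as well, the imputed date can even precede first dose. Death and progression dates are protected by cross-checks; these dates are not.

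**Working it through.** The documents give no figure for the effect of this rule, so there is none to reproduce. The inputs are the default rule (SAP 8.1.2), the censoring row (SAP Table 7.5.2.8-1), scans every 6 weeks in the first 12 months (Protocol Table 5.1-2) and n = 110 (SAP 5). The lag from progression to therapy and the number of incomplete dates are not given. The lag is therefore assumed over a range, and every share below is conditional on an incomplete date.

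**Only the day missing.** Let L be the lag in days. The imputed date precedes the progression when the progression falls after the 15th and the therapy falls in the same month. With an average month of 30.44 days, about 15.44 days follow the 15th, so

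share ≈ max(0, 15.44 − L) / 30.44.

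Enumerating progression days over 2016 to 2018 gives the middle column. The formula agrees: L = 3 gives 12.44/30.44 = 0.409, and L = 7 gives 8.44/30.44 = 0.277.

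**Day and month missing.** The order is reversed when progression falls after 1 July and therapy falls in the same year: share ≈ (183 − L)/365.25. L = 1 gives 182/365.25 = 0.498; L = 21 gives 162/365.25 = 0.444.

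| Lag (days) | Day missing | Day and month missing |
|---|---|---|
| 1 | 47% | 50% |
| 3 | 41% | 49% |
| 7 | 28% | 48% |
| 10 | 18% | 47% |
| 14 | 5% | 46% |
| 21 | 0% | 44% |

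Averaged over lags of 1 to 28 days the day-missing share is 13%; over 14 to 28 days it is 0.5%. For lags of at least one day, the imputed date lies at most 15 days before progression if the day is missing, and at most 182 days if the month is missing too.

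**Worked case.** Progression on the 20 March scan, SRT on 27 March recorded as March. The imputed date is 15 March, 5 days before the progression. The 20 March event becomes a censoring at the previous scan, 6 weeks back on schedule.

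**First dose.** With day and month missing, 1 July falls before first dose in 23% of cases if therapy occurs 3 to 26 weeks after first dose, 11% for 3 to 52 weeks and 5% for 3 to 104 weeks. With only the day missing and therapy at least 3 weeks after first dose, it is 0%.

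**Size on PFS (illustration, assumed data).** Take 110 subjects with 20, 14, 8 and 6 events at Weeks 6, 12, 18 and 24. True 24-week PFS is 62/110 = 56.4%. Move k events, split over the first two scans, to censorings before the scan concerned:

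- k = 1: 62/109 = 56.9%
- k = 3: (90/108) × (76/89) × (62/76) = 58.1%
- k = 5: (90/107) × (76/88) × (62/76) = 59.3%

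**Primary clinical benefit rate (CBR).** SAP 4.1 bases the primary analysis on the BOR entered on the case report form, then adjusted. The two adjustments that compare progression with the therapy date move a not-evaluable BOR, or stable disease of under 6 months, to progressive disease. None of these three categories counts as benefit, so failing the condition leaves CBR unchanged. The adjustment for complete and partial responses does not use the therapy date. CBR can move only if a programmer re-applies the SAP 4.1 window to scans. Example: first dose 1 January 2018, stable disease throughout, a scan on 23 July at (203 + 1)/30.4375 = 6.70 months, radiotherapy on 30 July recorded as July. Imputed to 15 July, it excludes that scan and leaves the Week 24 scan of 18 June at (168 + 1)/30.4375 = 5.55 months. One such subject is 1/110 = 0.9 points.

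**The case against.** Four points on the other side carry weight.

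- **Scope is an inference.** The external medication specification is not available, and no passage says which data domain holds radiotherapy and surgery. Separate reporting lines in SAP 7.5.2.7 do not settle storage. SAP 8.1.2 also says only that its conventions may be used. This stands, and the point is conditional on it. If the specification does cover these dates, the SAP should say so.
- **On-study SRT dates are likely to be complete.** Study drug is interrupted for SRT and resumes only after a defined observation period and steroid taper (Protocol Synopsis and Section 4.5.2.1). Incomplete dates are more plausible for later therapy reported by phone, when many subjects will already have progressed. This stands and limits the likely number.
- **Lags may be long.** Protocol 5.4 calls for a confirming MRI about 4 weeks after suspected progression, and at that lag the day-missing rule reverses nothing. This stands in part: Protocol 5.4.3 asks for verification only when progression is equivocal, and a long lag does not rescue a date with the month missing.
- **Data cleaning would catch** a therapy date before first dose. That is likely, but the SAP does not say so, and a reversal of a few days around progression would be less visible.

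A reader might go further and infer that the primary CBR is biased through the SAP 4.1 adjustments. The documents do not support that, for the reason given in the working: the therapy-date conditions only move subjects among categories that are not benefit.

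**Conclusion.** The gap holds, and its severity is minor. On the visible text, and assuming the external medication specification does not cover them, incomplete radiotherapy and surgery dates go to the 15th or 1 July unchecked. Therapy given soon after a progression can then be dated before it, which biases the secondary PFS estimates upward.

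The size per incomplete date depends on the assumed lag: 41% reversed at 3 days, falling to 0% at 21 days, if only the day is missing; 44% to 50% for lags of 1 to 21 days if the month is missing too. With no count of incomplete dates, the total effect cannot be computed and is probably small. An effect on primary CBR exists only if the BOR window is re-applied to scan data with the imputed date. The plan does not support reading these percentages as the share of all subjects affected.

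**What to change.** In SAP 8.1.2, name the dates of radiotherapy and surgery given as subsequent therapy and state their rule:

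- Keep the 15th, or 1 July.
- For therapy known to be on or after study start, set the imputed date no earlier than first dose.
- If a documented progression in the compartment being analysed (intracranial, extracranial or global) falls in the same recorded month or year, set the imputed date no earlier than that progression. The same day suffices, because Table 7.5.2.8-1 keeps a same-day progression as an event.
- List all imputed therapy dates. Repeat PFS with the earliest and latest possible therapy dates, and CBR too if the BOR window is applied to scans.

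The bound takes the reversed share to zero for therapy truly given on or after progression. It does not alter the main result in the CBR example, where no progression falls in the month; the earliest and latest dates cover that case. The cost is a few sentences and a few lines of derivation. The one downside is that therapy truly given before a progression in the same period would be counted as after it. That keeps the event and is conservative for PFS.

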9 CONTENT OF REPORTS

The complete list of analyses contributing to the clinical study report is given in the Data Presentation Plan.

[REDACTED]

APPENDIX 1 SELECT ADVERSE EVENTS DEFINITION AND CONVENTIONS

The select AEs consist of a list of PT grouped by specific category (e.g. pulmonary events, gastrointestinal events categories) and by subcategory (e.g. thyroid disorders, diabetes, pituitary, adrenal disorders subcategories). These categories and subcategories are defined by the Sponsor and the list that is most current at the time of analysis will be used. Also changes may be made to this list with each new version of MedDRA.

For information, the select AEs defined at the time of finalization of the first version of the document are listed in Table 11-3 using MedDRA version 16. The final list used for the clinical study report will be included in an Appendix of the CSR.

Time-to onset definition

Time-to onset of select AE (any grade) for a specific category (i.e. pulmonary events, gastrointestinal events, ...) is defined as the time between the day of the first dose of study treatment and the onset date of the earliest select AE (of any grade) in this category.

If the subject did not experience a select AE (of any grade) in the category, time-to onset will be censored at the maximum follow-up time of all subjects in their respective treatment group (i.e. for subjects without an event, follow-up time is defined from first dosing date up to last dosing date +30 days (or 100 days depending on the analysis) if subjects are off treatment and followed for at least 30 days (or 100 days depending on the analysis) , otherwise it is defined up to the last known alive date). The resulting Kaplan-Meier plot will represent the cumulative rate of the select AE (any grade) in the category over time.

Time-to onset of select AE (grade 3-5) for a specific category is defined similarly but restricted to grade 3-5 select AEs.

Time-to onset of drug-related (grade 3-5 or any grade) select AE for a specific category is defined similarly but restricted to drug-related select AEs.

Time-to onset for a specific subcategory is defined similarly but restricted to event of this subcategory.

Time-to resolution definition

In order to derive the time-to resolution, overlapping or contiguous select AEs within a specific category (defined in Table 11-3) will be collapsed into what will be termed “clustered” select AEs. For example, if a subject (without pre-treatment AE) experienced an AE from 1st to 5th January, another AE (with different PT but within same category) from 6th to 11th January and same AE from 10th to 12th January, these will be collapsed into one clustered select AE from 1st to 12th January. Table 11-2 is summarizing key derivation steps for each type of clustered select AEs.

Time-to resolution of select AE (any grade) for a specific category is defined as the longest time from onset to complete resolution or improvement to the grade at baseline among all clustered select AEs in this category experienced by the subject. Events which worsened into grade 5 events (death) or have a resolution date equal to the date of death are considered unresolved. If a clustered

select AE is considered as unresolved, the resolution date will be censored to the last known date alive. Improvement to the grade at baseline implies that all different AE events in the clustered select AE should at least have improved to the corresponding (i.e. with same PT) baseline grade. This measure is defined only for subjects who experienced at least one select AE in the specific category.

The time-to resolution of select AE (grade 3-5) for a specific category is defined similarly with an onset date corresponding to a grade 3-5 select AE.

Time-to resolution of drug-related select AE (any grade or grade 3-5) is defined similarly but restricted to drug-related select AE.

The time-to resolution of select AE (any grade or grade 3-5, drug-related or all) where immune modulating medication was initiated is defined similarly with the additional condition that the subject started an immune modulating medication during the longest select AE resolution period.

Time-to resolution for a specific subcategory is defined similarly but restricted to event of this subcategory.

Table 11-2: Derivation of clustered select AE

Type of clustered select AE	Derivation
Any grade	Collapse any on-treatment select AE from the same category
Drug-related of any grade	Collapse any on-treatment drug-related select AE from the same category
Grade 3-5	Collapse any on-treatment select AE from the same category. Resolution will be based on the onset date of the earliest grade 3-5 records (if no grade 3-5 record, clustered select AE is excluded)
Drug-related of Grade 3-5	Collapse any on-treatment drug-related select AE from the same category Resolution will be based on the onset date of the earliest grade 3-5 record (if no Grade 3-5 record, clustered select AE is excluded)

The algorithm for collapsing select AE records is using the following conventions:

For each subject and specified category, the corresponding AE records will be collapsed when:

- 1) Multiple AE records have the same onset date.
- 2) The onset date of an event record is either the same day or 1 day later than the resolution date of a preceding event record (contiguous events).
- 3) The onset date of an event record is after the onset date and prior to or on the resolution date of a preceding event record (overlapping events).

Table 11-3: Select Adverse Events

Category	Subcategory	Preferred Terms
Endocrine Adverse Events	ADRENAL DISORDER	ADRENAL
		ADRENAL SUPPRESSION
		ADRENAL INSUFFICIENCY ACUTE
		BLOOD CORTICOTROPHIN DECREASED
		BLOOD CORTICOTROPHIN INCREASED
		HYPOTHALAMIC PITUITARY ADRENAL AXIS SUPPRESSION
		PRIMARY ADRENAL INSUFFICIENCY
		SECONDARY ADRENOCORTICAL INSUFFICIENCY
	DIABETES	DIABETES MELLITUS
		DIABETIC KETOACIDOSIS
		DIABETIC KETOSIS
		FULMINANT TYPE 1 DIABETES MELLITUS
		LATENT AUTOIMMUNE DIABETES IN ADULTS
		TYPE 1 DIABETES MELLITUS
	PITUITARY DISORDER	HYPOGONADISM
		HYPOPHYSITIS
		HYPOPITUITARISM
		LYMPHOCYTIC HYPOPHYSITIS
	THYROID DISORDER	ATROPHIC THYROIDITIS
AUTOIMMUNE HYPOTHYROIDISM		
AUTOIMMUNE THYROID DISORDER		
AUTOIMMUNE THYROIDITIS		
BASEDOW'S DISEASE		
BLOOD THYROID STIMULATING HORMONE DECREASED		
BLOOD THYROID STIMULATING HORMONE INCREASED		
HYPERTHYROIDISM		
HYPOPARATHYROIDISM		
HYPOTHYROIDISM		
IMMUNE-MEDIATED HYPERTHYROIDISM		
IMMUNE-MEDIATED HYPOTHYROIDISM		
IMMUNE-MEDIATED THYROIDITIS		
PRIMARY HYPERTHYROIDISM		
PRIMARY HYPOTHYROIDISM		
SILENT THYROIDITIS		
THYROID FUNCTION TEST ABNORMAL		
THYROID HORMONES DECREASED		
THYROID HORMONES INCREASED		
THYROIDITIS		
THYROIDITIS ACUTE		
THYROXINE DECREASED		

Table 11-3: Select Adverse Events

Category	Subcategory	Preferred Terms
		THYROXINE FREE DECREASED THYROXINE FREE INCREASED THYROXINE INCREASED TRI-IODOTHYRONINE UPTAKE INCREASED
Hypersensitivity/Infusion Reactions		ANAPHYLACTIC REACTION ANAPHYLACTIC SHOCK BRONCHOSPASM HYPERSENSITIVITY INFUSION RELATED HYPERSENSITIVITY REACTION INFUSION RELATED REACTION
Gastrointestinal Adverse Events		COLITIS DIARRHOEA ENTERITIS ENTEROCOLITIS FREQUENT BOWEL MOVEMENTS GASTROINTESTINAL PERFORATION
Hepatic Adverse Events		ACUTE HEPATIC FAILURE ACUTE ON CHRONIC LIVER FAILURE ALANINE AMINOTRANSFERASE INCREASED ASPARTATE AMINOTRANSFERASE INCREASED AUTOIMMUNE CHOLANGITIS AUTOIMMUNE HEPATITIS BILIARY CIRRHOSIS BILIRUBIN CONJUGATED DECREASED BILIRUBIN CONJUGATED INCREASED BLOOD ALKALINE PHOSPHATASE INCREASED BLOOD BILIRUBIN INCREASED CHOLANGITIS DRUG-INDUCED LIVER INJURY GAMMA-GLUTAMYLTRANSFERASE INCREASED HEPATIC ENZYME INCREASED HEPATIC FAILURE HEPATITIS HEPATITIS ACUTE HEPATOTOXICITY HYPERBILIRUBINAEMIA IMMUNE-MEDIATED CHOLANGITIS

Table 11-3: Select Adverse Events

Category	Subcategory	Preferred Terms
		IMMUNE-MEDIATED HEPATIC DISORDER IMMUNE -MEDIATED HEPATITIS LIVER DISORDER LIVER FUNCTION TEST ABNORMAL LIVER FUNCTION TEST INCREASED LIVER INJURY TRANSAMINASES INCREASED
Pulmonary Adverse Events		ACUTE RESPIRATORY DISTRESS SYNDROME ACUTE RESPIRATORY FAILURE AUTOIMMUNE LUNG DISEASE HYPERSENSITIVITY PNEUMONITIS IDIOPATHIC INTERSTITIAL PNEUMONIA IMMUNE-MEDIATED PNEUMONITIS INTERSTITIAL LUNG DISEASE LUNG INFILTRATION PNEUMONITIS
Renal Adverse Events		ACUTE KIDNEY INJURY AUTOIMMUNE NEPHRITIS BLOOD CREATININE INCREASED CREATININE RENAL CLEARANCE DECREASED END STAGE RENAL DISEASE GLOMERULONEPHRITIS RAPIDLY PROGRESSIVE HYPERCREATININAEMIA NEPHRITIS NEPHRITIS ALLERGIC PARANEOPLASTIC GLOMERULONEPHRITIS RENAL FAILURE RENAL FAILURE ACUTE RENAL TUBULAR NECROSIS TUBULOINTERSTITIAL NEPHRITIS URINE OUTPUT DECREASED
Skin Adverse Events		ANAL ECZEMA AUTOIMMUNE BLISTERING DISEASE AUTOIMMUNE DERMATITIS BLISTER

Table 11-3: Select Adverse Events

Category	Subcategory	Preferred Terms
		BULLOUS HAEMORRHAGIC DERMATOSIS
		DERMATITIS
		DERMATITIS ACNEIFORM
		DERMATITIS ALLERGIC
		DERMATITIS ATOPIC
		DERMATITIS EXFOLIATIVE
		DRUG ERUPTION
		ECZEMA
		ENANTHEMA
		ERYTHEMA
		ERYTHEMA MULTIFORME
		ERYTHRODERMIC ATOPIC DERMATITIS
		EXFOLIATIVE RASH
		FIXED ERUPTION
		GUTTATE PSORIASIS
		IMMUNE-MEDIATED DERMATITIS
		MUCOCUTANEOUS DISORDER
		MUCOSA VESICLE
		NODULAR RASH
		PALMAR-PLANTAR ERYTHRODYSAESTHESIA SYNDROME
		PARADOXICAL PSORIASIS
		PEMPHIGOID
		PEMPHIGUS
		PHOTOSENSITIVITY REACTION
		PRURITUS
		PRURITUS ALLERGIC
		PSORIASIS
		PUSTULAR PSORIASIS
		PUSTULE
		RASH
		RASH ERYTHEMATOUS
		RASH MACULAR
		RASH MACULO-PAPULAR

Table 11-3: Select Adverse Events

Category	Subcategory	Preferred Terms
		RASH MORBILLIFORM
		RASH PAPULAR
		RASH PRURITIC
		RASH PUSTULAR
		RASH VESICULAR
		SJS-TEN OVERLAP
		SCROTAL DERMATITIS
		SKIN EXFOLIATION
		SKIN IRRITATION
		STEVENS-JOHNSON SYNDROME
		TOXIC EPIDERMAL NECROLYSIS
		TOXIC SKIN ERUPTION
		URTICARIA
		URTICARIAL DERMATITIS
		VITILIGO
		VULVAL ECZEMA
